1.2 BACKGROUND ON CRENEZUMAB

Crenezumab (RO5490245) is a fully humanized monoclonal antibody (MAb) based on a human IgG4 framework that contains heavy chain V_HIII and light chain V_κII subgroup sequences. In vitro, crenezumab binds to Aβ peptides, Aβ1-40 and Aβ1-42, in multiple forms (monomers, oligomers, fibrils, and plaques), and notably with high affinity to oligomers.

In vitro studies demonstrated the ability of crenezumab to block Aβ aggregation, promote Aβ disaggregation, and protect neurons from oligomer-induced cytotoxicity (Adolfsson et al. 2012). Its IgG4 backbone confers reduced activation of Fcγ receptor (FcγRs) in comparison with IgG1 and was shown to minimize FcγR-mediated activation of microglia and release of inflammatory cytokines upon oligomer engagement—which has also been proposed to contribute to neurotoxicity (Xing et al. 2011; Heneka et al. 2015) while preserving FcγR-mediated microglial phagocytosis of oligomers (Adolfsson et al. 2012). Following in vivo dosing in presenilin 2 (PS2) amyloid precursor protein (APP) transgenic (Tg) mice, crenezumab localizes to brain areas with putative high concentrations of Aβ oligomers, i.e., hippocampal mossy fibers and the periphery of amyloid plaques (Koffie et al. 2009; Liu et al. 2015) but not to the dense core of plaques or vascular amyloid. The neutralization and removal of Aβ oligomers is a rational approach to modify disease progression in AD.

Amyloid-related imaging abnormalities (ARIAs), indicative of vasogenic edema or effusions (ARIA-E) and microhemorrhages (mHs) or leptomeningeal hemosiderosis (*together referred to as* ARIA-H), have been reported in recent AD trials involving MAbs that bind aggregated forms of Aβ and have IgG1 backbones with fully preserved FcγR-mediated effector function (Salloway et al. 2009; Ostrowitzki et al. 2012; Fuller et al. 2014; Sevigny et al. 2015). As these molecules demonstrated increases in ARIA-E incidence with increasing dose and apolipoprotein E4 (APOE4) allele frequency, the dose levels administered in past trials have been constrained to limit these events (Salloway et al. 2009). Crenezumab was designed as an IgG4 on the basis of the hypothesis that reducing effector function—shown to minimize FcγR-mediated activation of microglia and release of inflammatory cytokines upon oligomer engagement—would lower the risk of inducing ARIA-E and ARIA-H, possibly by minimizing inflammation at brain vasculature (Wilcock et al. 2006). A lack of binding for crenezumab to vascular amyloid, noted following in vivo dosing in PS2APP Tg mice (GNE Study 15-2817B), may additionally reduce the risk of ARIA.

The safety profile of crenezumab to date (see Section 1.2.3) allows a higher dose of crenezumab than the 300 mg SC every 2 weeks (Q2W) or the 15 mg/kg IV Q4W that were used in the Phase II studies to be used in the *parent* BN29552 and BN29553 Phase III *studies* (i.e., 60 mg/kg IV crenezumab). This dose selection is supported by the data from the Phase Ib GN29632 study that investigated higher doses than those in Phase II, including 60 mg/kg and 120 mg/kg IV Q4W. The aim of the high dose is to

achieve higher systemic exposure and therefore higher brain concentrations, which are predicted to result in greater efficacy than seen in the completed Phase II studies.

See the Crenezumab Investigator's Brochure for details on nonclinical and clinical studies.

1.2.1 Summary of Nonclinical Studies

In vivo pharmacology and CNS distribution studies were conducted in human amyloid precursor protein (hAPP)-Tg mouse models of AD. Crenezumab was detected in both brain homogenates and cerebrospinal fluid (CSF) following a single IV dose. Administration of two weekly doses of 5 mg/kg crenezumab to hAPP-Tg mice decreased total A β levels in soluble fractions of brain homogenates and increased plasma total A β levels. An in vivo pharmacology study in PS2APP Tg mice showed via immunofluorescence microscopy that crenezumab localized to brain areas with putatively high concentrations of A β oligomers, i.e., hippocampal mossy fibers and the periphery of amyloid plaques, but not to the dense core of plaques or vascular amyloid.

The pharmacokinetics and toxicokinetics of crenezumab were studied in hAPP-Tg mice, non-Tg mice, and cynomolgus monkeys. Studies demonstrated biphasic disposition characterized by a short distribution phase followed by a long elimination phase of crenezumab. Due to presence of anti-drug antibody (ADA) there were less than dose-proportional increases in overall crenezumab exposure across the range of doses investigated in mice. In monkeys, repeat dosing also resulted in development of ADA in a proportion of animals that correlated with a trend toward slightly lower serum concentrations of crenezumab, but did not affect dose-proportional increases in exposure. In both species, dose-related increases in plasma total A β levels were observed and appeared to correlate well with serum crenezumab concentrations. In mice, following a single IV administration, crenezumab was observed in both brain and CSF.

Toxicity studies of crenezumab were conducted in cynomolgus monkeys. IV administration of crenezumab to cynomolgus monkeys for 4 weeks at one dose per week (a total of five doses) was well tolerated at doses up to 50 mg/kg. In a subsequent chronic toxicity study, SC administration of crenezumab to cynomolgus monkeys for 39 weeks (a total of 40 doses) was well tolerated at doses up to 100 mg/kg per week (the highest dose tested). No observations related to crenezumab administration were seen on expanded histopathology evaluation of the brain. Nonclinical safety data provide 2-, 3-, and 6-fold safety factors for the 60-mg/kg dose at steady-state on the basis of human equivalent dose, exposure (area under the concentration-time curve [AUC]), and maximum concentration (C_{max}), respectively, relative to the maximum tested dose of 100 mg/kg via SC administration in cynomolgus monkeys (see the Crenezumab Investigator's Brochure).

A study to further evaluate the pharmacology of crenezumab in hAPP-Tg mice included weekly or monthly intraperitoneal (IP) administration of crenezumab for 16 weeks (a total of 17 weekly doses or 5 monthly doses) at doses up to 50 mg/kg. When crenezumab was given at doses > 10 mg/kg for > 2 weekly or monthly doses, unexpected deaths were observed. No microscopic findings were identified in the CNS or peripheral tissues to explain the mortalities. A high incidence of anti-crenezumab antibodies was observed (93% of animals evaluated), which resulted in attenuation of both serum crenezumab concentrations and pharmacodynamic (PD) responses (plasma total A β ₁₋₄₀ and A β ₁₋₄₂). These data suggest that these unexpected deaths were likely the result of an adverse immunogenic response (i.e., anaphylaxis) to the xenogeneic humanized crenezumab antibody in mice and are therefore unlikely to be predictive of human safety risk.

To address potential safety concerns associated with administration of anti-A β antibodies in the AD population (i.e., ARIA-E and -H), additional studies were performed in Tg mouse models of AD (hAPP or hAPP/presenilin 1 [PS-1]) to evaluate for vascular injury (e.g., cerebral mH). These studies were performed with PRO300491, a human/mouse chimeric anti-A β MAb that shares a humanized variable domain with crenezumab but has the murine IgG2a constant domain with D265A and N297A mutations. This reverse chimera antibody (PRO300491) and crenezumab demonstrate comparable binding affinity to human A β ₁₋₄₀ and A β ₁₋₄₂ peptides. The murine IgG2a Fc was selected to decrease immunogenic potential in mice, as crenezumab appeared to be highly immunogenic in hAPP-Tg and non-Tg wild-type mice. Furthermore, the Fc mutations D265A and N297A were designed to decrease binding to murine Fc γ R and to approximate the reduced effector function of an IgG4 antibody (Shields et al. 2001).

A weekly repeat-dose study was conducted in hAPP/PS1-Tg mice with PRO300491 for 4 weeks (a total of four doses). At IV doses up to 60 mg/kg, PRO300491 was well tolerated and no treatment-related increases in mH were observed. In a subsequent chronic toxicity study, weekly IP administration of PRO300491 to hAPP-Tg mice for 24 weeks (a total of 25 doses) was well tolerated at doses up to 50 mg/kg. No changes in the cerebral microvasculature (e.g., mH or amyloid deposition) were observed despite evidence of sustained antibody exposure and PD activity (plasma total A β ₁₋₄₀). These findings support the hypothesis that A β antibodies with reduced effector function, such as crenezumab, are well tolerated in hAPP-Tg mice and are not associated with the development of adverse effects similar to those described in the literature for other A β antibodies.

Overall, the nonclinical studies demonstrated that crenezumab has an acceptable pharmacokinetic (PK) and safety profile to support long-term SC or IV dosing in patients.

1.2.2 Summary of Clinical Studies

To date, crenezumab has been investigated in a total of 12 completed or ongoing *Roche-sponsored* Phase I, Phase II, and Phase III clinical trials. Approximately

1051 patients and healthy volunteers have been exposed to crenezumab in these studies.

Four Phase I studies (Studies ABE4427g, AB4662g, GP29172, and [REDACTED] have been completed. Study ABE4427g studied the safety, tolerability, and pharmacokinetics of single- and multiple-ascending doses of IV crenezumab in patients with mild to moderate AD who were 50–86 years of age. Study ABE4662g studied the pharmacokinetics of IV and SC dosing and the relative bioavailability of crenezumab (SC dosing) in healthy volunteers who were 18–50 years of age. Study GP29172 evaluated the pharmacokinetics of SC dosing and the bioequivalence of two formulations of crenezumab (SC dosing) in healthy volunteers who were 18–65 years of age.

[REDACTED]

Two Phase I studies (GN29632 and [REDACTED] are ongoing. Study GN29632 is a dose-escalation study with a 13-week double-blind treatment period (DBTP) followed by an ongoing open-label all-to-active extension designed to assess safety, tolerability, and pharmacokinetics of multiple doses of crenezumab in patients with mild to moderate AD with doses of 30, 45, 60, and 120 mg/kg IV Q4W. [REDACTED]

[REDACTED]

The Phase II program (ABE4869g and ABE4955g), including an OLE study (GN28525), was designed to study safety and tolerability and to assess the clinical and biomarker effects of crenezumab in an AD dementia population (50–80 years of age) with mild to moderate disease severity (Mini Mental State Examination [MMSE] score, 18–26) (completed Studies ABE4869g and ABE4955g tested two doses of crenezumab [300 mg SC Q2W and 15 mg/kg IV Q4W versus placebo over 18 months]). The OLE study (GN28525) in patients who previously participated in either Study ABE4869g or ABE4955g *is complete*.

Another *Phase II* efficacy study in a different population within the AD spectrum (Study GN28352) is also ongoing. This study is conducted in a pre-symptomatic at-risk-for-AD population (30–60 years of age) with an autosomal dominant mutation (E280A) in the *PS1* gene (autosomal dominant AD [ADAD] population). This study initially dosed crenezumab at 300 mg SC Q2W. (Following results from the above-mentioned Phase II studies, the dose was increased to 720 mg SC Q2W.) In order to maintain the blind for the mutation, a group of mutation non-carriers who only receive placebo is also included.

There are two ongoing Phase III studies evaluating the efficacy, safety, and tolerability of crenezumab at a dose of 60 mg/kg IV Q4W versus placebo in a pAD to mAD population (MMSE score, 22–30). Study BN29552 (CREAD) and BN29553 (CREAD2) are randomized, double-blind, parallel-group, placebo-controlled trials designed to evaluate the safety and efficacy of crenezumab in patients aged 50–85 years who meet protocol-specified criteria for pAD or mAD.

China Extension Phase (DBTP)

Following completion of the global enrollment phase of Study BN29553, additional patients will continue to be enrolled in a China extension phase (i.e., China extension to the main Phase III study BN29553) to ensure a total enrollment sufficient to support registration in the People's Republic of China. This China subpopulation may include patients enrolled at sites in China during both the global enrollment phase and the China extension phase and could be included in this OLE, if applicable.

The objective of the China extension phase and the China subpopulation analyses is to assess the treatment effects of crenezumab in a population of patients in the People's Republic of China and to investigate the consistency in treatment effects between the China subpopulation and the global population for the purpose of registration in the People's Republic of China.

For a summary and details of the clinical studies to date refer to the Crenezumab Investigator's Brochure for further information.

1.2.3 Safety Overview

The clinical safety of crenezumab has been evaluated using all available clinical data from the four completed Phase I studies (ABE4427, ABE4662g, GP29172, and [REDACTED] three completed Phase II studies (ABE4869g, ABE4955g, and GN28525), two ongoing Phase I studies ([REDACTED] and GN29632), one ongoing Phase II study (GN28352), and two ongoing Phase III studies (BN29552 and BN29553).

In the Phase II studies in mild to moderate AD, more fatal events and *events of* pneumonia were reported in crenezumab-treated patients than in placebo-treated patients. However, the rates of death and pneumonia in the crenezumab arms were within the expected rates for the enrolled population. Please refer to Sections [1.2.3.2](#) and [1.2.3.3](#), respectively, for more information.

ARIA-E and ARIA-H remain potential *risks* for crenezumab, even if they were not identified as a safety concern in crenezumab studies:

- ARIA-E and ARIA-H have been observed with other MAbs that target A β ; specifically, ARIA-E events have been dose limiting for several anti-A β antibodies (see Section [1.2.3.4](#)).

- In the crenezumab Phase II program, the overall rate of ARIA-E in the DBTP was 1/349 (0.3%) in crenezumab-treated versus 0/173 in placebo-treated patients. The incidence of ARIA-H was similar between crenezumab- and placebo-treated patients: The number of patients with incident mH was 40/349 (11.5%) in crenezumab-treated and 22/173 (12.7%) in placebo-treated patients, while superficial siderosis of CNS was reported in 3 patients (1.7%) receiving placebo. The rate of ARIA-E and ARIA-H in the DBTP of the Phase II program is similar to the background rate in the mild to moderate AD population (0.2% – 0.4%) (Doody et al. 2014; Salloway et al. 2014).
- *As of the date of release of this protocol, 4 patients have developed ARIA-E across the crenezumab program. In one patient, ARIA-E was considered symptomatic (headache).*

Injection- and infusion-site reactions have been reported at similar rates in patients receiving crenezumab SC or IV and placebo *in the Phase II studies.*

1.2.3.1 Adverse Event Profile

The Phase II program in mild to moderate AD (Studies ABE4869g and ABE4955g) consists of the largest completed studies conducted to date with crenezumab.

The DBTP of the Phase II program in mild to moderate AD was defined as the protocol-specified reporting period of the 2:1 randomization IV and SC dose arms of Studies ABE4869g and ABE4955g. The DBTP excluded the safety run-in arm of Study ABE4869g.

In the DBTP, patients were treated over a 68-week period and monitored for safety for 4 additional weeks if they rolled over into Study GN28525 or for 16 weeks if they did not enter Study GN28525 or they discontinued treatment prematurely. The observation period included the 68-week treatment period and the safety follow-up period.

The safety evaluable database for the Phase II program included 535 patients with mild to moderate AD who received at least one dose of study drug. Of these, 522 patients had been randomized to receive crenezumab at either 300 mg Q2W SC (N=148) or 15 mg/kg Q4W IV (N=198) or to receive placebo (N=176). During the DBTP of the Phase II program, 9 patients (2.6%) who received crenezumab and 9 patients (5.1%) who received placebo withdrew because of adverse events. There were no imbalances in the overall rates of adverse events between patients who received crenezumab and patients who received placebo (91.1% [N=318] vs. 90.8% [N=157], respectively). Serious adverse events were reported in 57 patients (16.3%) who received SC or IV crenezumab and in 21 patients (12.1%) who received SC or IV placebo. The imbalance in the rate of serious adverse events was mainly due to reports of pneumonia (see Section 1.2.3.3).

In the completed OLE study of the Phase II program (Study GN28525), a total of 93.2% of patients from the original SC cohort and 87.7% of patients from the original IV cohort experienced at least one adverse event. Reported adverse events were as expected in an elderly population with AD, with falls and urinary tract infections being the most frequently recorded adverse events.

Details on the safety data from all completed and ongoing trials with crenezumab are provided in the most recent version of the Crenezumab Investigator's Brochure.

1.2.3.2 Deaths

During the DBTP of the Phase II program, 5 patients died. All five deaths occurred in patients treated with crenezumab; none was assessed by the investigator as related to study drug. This represents 1.4% of patients who received crenezumab compared with 0% of patients who received placebo. The rate of death in the crenezumab arms was within the expected rates of death in the AD clinical trial population treated with placebo (0%–1.9%) or with A β -directed passive immunotherapy (2.1%–2.4%; Salloway et al. 2009, 2014; Doody et al. 2014).

In the OLE study GN28525, 15 patients (4.2%) died. Ten of the 15 patients had received active crenezumab, and 5 patients had received placebo. This represents 4.0% of patients who received crenezumab compared with 4.5% of patients who received placebo during DBTP of the Phase II study. All deaths were assessed as not related to study drug by the investigator.

Details on deaths reported in the completed and ongoing clinical studies with crenezumab are presented in the most recent Crenezumab Investigator's Brochure.

1.2.3.3 Pneumonia

An imbalance in the rates of serious adverse events of pneumonia was observed in the DBTP of the Phase II program, with 6 cases (1.7%) in the crenezumab arms and 1 case (0.6%) in the placebo arms. All serious pneumonia cases occurred 7–13 months after the first study dose. Individual cases were confounded by age, smoking history, diabetes, obesity, some by previous pneumonia events, and tuberculosis, which are known risk factors for developing pneumonia. An imbalance in non-serious adverse events of total lower respiratory tract infection, also driven by pneumonia, was observed in the DBTP of the Phase II program, with 5 cases versus 0 cases (1.4% vs. 0%) of non-serious pneumonia observed in the crenezumab and placebo arms, respectively.

The diagnosis of pneumonia was confirmed by chest radiology in 5 of the 11 cases reported in crenezumab-treated patients. The vast majority of cases resolved upon standard treatment with antibiotics and in the absence of modification of the study drug regimen.

Overall, the pneumonia rates observed in the DBTP of Studies ABE4869g and ABE4955g (3.2% total and 1.7% serious) were slightly higher than those observed among Phase III AD clinical trial populations (Henley et al. 2012; Doody et al. 2014; Salloway et al. 2014; Henley et al. 2015). The pneumonia rates in the placebo-treated population were slightly lower (0.6%; Henley et al. 2012; Doody et al. 2014; Salloway et al. 2014; Henley et al. 2015). However, the precision of these estimates is limited by the relatively smaller sample size in crenezumab Phase II data compared with Phase III safety populations in bapineuzumab, solanezumab, and semagacestat studies. The rate of pneumonia in crenezumab-treated patients (3.2%) is within the reported incidence of pneumonia in the elderly population (2.5%–4.4%; Vila-Corcoles et al. 2009). The frequency and details of pneumonia events from all ongoing and completed studies is provided in the most recent version of the Crenezumab Investigator's Brochure.

1.2.3.4 ARIA-E and ARIA-H

In the DBTP of the Phase II program in mild to moderate AD, a single case of asymptomatic ARIA-E was reported in a patient who received crenezumab. *This patient experienced asymptomatic recurrences during the OLE phase.* The proportion of patients with ARIA-H was similar in the crenezumab and placebo arms: new (incident) mHs were documented in 11.5% (N=40) of crenezumab-treated patients and 12.7%

(N=22) of placebo-treated patients. The proportion of patients with superficial siderosis of CNS was 0% in crenezumab-treated patients versus 1.7% (N=3) in placebo-treated patients. All findings in crenezumab-treated patients were asymptomatic.

An overview of ARIA-H and ARIA-E cases from all ongoing and completed studies is provided in the most recent version of the Crenezumab Investigator's Brochure.

1.2.3.5 Summary

The safety and tolerability profile of crenezumab to date supports its continued development in AD.

More fatal events and pneumonia cases *were* observed during the DBTP of the Phase II program in crenezumab-treated versus placebo-treated patients. There was no pattern seen in the causes of death and no obvious mechanism linking crenezumab treatment with pneumonia (e.g., no evidence of immunosuppression). Importantly, there was no relationship between steady-state exposure (AUC or C_{max}) and safety events within each dose cohort. In addition, rates of death and pneumonia in crenezumab-treated patients were within the expected ranges for the elderly AD population.

Further details are presented in the Crenezumab Investigator's Brochure.

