1.3.7 Overall Benefit–Risk Summary

The overall benefit–risk profile of investigation of crenezumab at a dose of 60 mg/kg IV Q4W in a population of pAD to mAD patients is favorable.

Overall, the benefit–risk assessment of crenezumab is based on the following.

In Phase II studies (DBTP):

- The primary endpoints were not met.
- In further analyses, a consistent effect on cognitive scales including the Alzheimer's Disease Assessment Scale–Cognition 12 (ADAS-Cog12) scale was observed in patient subsets with mild disease who were treated with crenezumab 15 mg/kg IV Q4W versus placebo.
 - A 4-fold higher dose is being investigated in Phase III studies, including this OLE. A higher dose than that used in the Phase II program is expected to result in increased brain exposure and thus in increased target engagement and has the potential for better efficacy.
- Treatment with crenezumab was associated with an increase in CSF-A β_{42} relative to placebo, which was suggestive of target engagement in the CNS.
- While more deaths and pneumonia cases were observed with crenezumab than with placebo, there was no pattern seen in the causes of death, and no obvious common mechanism observed for pneumonia (e.g., immunosuppression). In addition, death rates are in line with background rates for the placebo-treated or untreated AD population (Henley et al. 2015) and in the variability range reported in clinical trials for compounds of this class with similar patient populations and durations of treatment (Doody et al. 2014; Salloway et al. 2014). The rate of

pneumonia in crenezumab-treated patients (3.2%) is within the reported incidence of pneumonia in the elderly population (2.5%–4.4%; Chong and Street 2008) and is slightly higher than the rate of pneumonia cases reported in the active and placebo arms of the solanezumab Phase III trials (2.0% and 2.1%, respectively; Doody et al. 2014). This may be attributable to the small patient numbers in the Phase II studies.

The benefit–risk assessment of crenezumab is also based on the following.

- Pneumonia cases, other serious respiratory infections, and deaths will be closely monitored in the study, with the requirement to report these cases to the Sponsor within 24 hours with a full description of the case (see Section 5.3.5).

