6.4 SAFETY ANALYSES

The safety analysis population will include all patients who completed the DBTP and received at least one dose of study drug in either Study BN29552 or BN29553 and entered the OLE study. Patients will be grouped according to the treatment actually received until the first visit of the OLE study.

- Incidence, nature, and severity of adverse events
- Incidence, nature, and severity of serious adverse events
- Incidence of adverse events of special interest
- Incidence and nature of MRI safety findings: ARIA-E and ARIA-H
- Incidence of treatment discontinuations due to adverse events
- Mean changes in clinical laboratory tests from baseline over time, incidence of treatment-emergent abnormal laboratory values, and abnormal laboratory values reported as adverse events
- Mean change in ECG assessments from baseline over time and incidence of abnormal ECG assessments
- Incidence of immunogenicity as evidenced by antibodies to crenezumab or other components of drug product
- Mean change in vital signs (blood pressure, heart rate) from baseline over time and incidence of abnormal vital sign measurements
- Changes in CSSR-S scores from baseline over time.

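### The safety summaries call the Phase II pneumonia rate expected for AD patients although the protocol's own AD-trial figures are lower, and Section 6.4 plans no exposure-adjusted pneumonia rate for the extension

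*Combined protocol and SAP*

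**What the plan says.** Two summary statements in the protocol describe the Phase II pneumonia rate as expected. Section 1.2.3 says that "the rates of death and pneumonia in the crenezumab arms were within the expected rates for the enrolled population". Section 1.2.3.5 says that "rates of death and pneumonia in crenezumab-treated patients were within the expected ranges for the elderly AD population".

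The detailed sections say something different. Section 1.2.3.3 reports serious pneumonia "with 6 cases (1.7%) in the crenezumab arms and 1 case (0.6%) in the placebo arms" and non-serious pneumonia "with 5 cases versus 0 cases (1.4% vs. 0%) of non-serious pneumonia observed in the crenezumab and placebo arms". It states that the crenezumab rates (3.2% total, 1.7% serious) "were slightly higher than those observed among Phase III AD clinical trial populations", and then places 3.2% within a range of 2.5% to 4.4% for the elderly population. Section 1.3.7 repeats that range, calls 3.2% "slightly higher than the rate of pneumonia cases reported in the active and placebo arms of the solanezumab Phase III trials", and gives those rates as 2.0% and 2.1%. Neither section gives an interval, although both mention small numbers.

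For the extension, Section 2 names pneumonia among the endpoints of the primary safety objective. Section 6.4 lists "Incidence of adverse events of special interest", with patients grouped by the treatment received before the extension. Section 6 says that safety data are summarised descriptively. Section 3.3 lets follow-up vary: patients may stop early and be followed for 16 weeks, while the first patient in may be treated for about 4 years.

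**The concern.** The summaries attach the AD population to a range that the protocol gives only for elderly people in general. Every AD-specific pneumonia figure in the document lies below 3.2%. Someone who reads only the summaries would conclude that the rate is ordinary for AD patients. Someone who reads the detail would conclude that it is somewhat high and imprecisely estimated. The extension uses a dose with about 4-fold the exposure of the higher Phase II dose (Section 1.3.4), so the background statement on this event should be exact.

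The second part concerns what the extension will deliver. Every patient receives crenezumab, so a pneumonia result can be interpreted only against something outside the study. A percentage of patients with an event, taken over follow-up of very different lengths, has no counterpart to be compared with. As written, Section 6.4 asks for neither patient-years nor an interval.

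**Working it through.** **Inputs.** Pneumonia counts come from Section 1.2.3.3: 6 serious and 5 non-serious cases on crenezumab (11 in total), and 1 serious and 0 non-serious on placebo. The denominators, 349 and 173, are those used for ARIA in Section 1.2.3. Benchmarks: 2.5% to 4.4% for the elderly (Sections 1.2.3.3 and 1.3.7), and 2.0% and 2.1% in AD trials (Section 1.3.7). Deaths: 5 versus 0, against a cited AD-trial placebo range of 0% to 1.9% (Section 1.2.3.2). Assumption: 11 cases are 11 patients.

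**The plan's own figures reproduce.** 11/349 = 3.15%; 6/349 = 1.72%; 5/349 = 1.43%; 1/173 = 0.58%. All match the stated 3.2%, 1.7%, 1.4% and 0.6%.

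**Missing intervals (exact Clopper-Pearson, 95%).**

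| Event | x/n | Rate | 95% CI |
|---|---|---|---|
| Total pneumonia, crenezumab | 11/349 | 3.2% | 1.6% to 5.6% |
| Serious pneumonia, crenezumab | 6/349 | 1.7% | 0.6% to 3.7% |
| Total pneumonia, placebo | 1/173 | 0.6% | 0.01% to 3.2% |
| Deaths, crenezumab | 5/349 | 1.4% | 0.5% to 3.3% |

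With the randomised numbers in Section 1.2.3.1 (148 + 198 = 346 on crenezumab), 11/346 gives the same 3.2% (1.6% to 5.6%).

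**Against each benchmark.**
- General elderly, 2.5% to 4.4%: the estimate is inside and the upper limit of 5.6% is above the top of the range.
- AD trials, 2.0% and 2.1%: the estimate is above. The upper limit is 5.57/2.1 = 2.7 to 5.57/2.0 = 2.8 times these rates, but the lower limit of 1.6% is below them. If the true rate were 2.0% or 2.1%, the chance of 11 or more cases in 349 would be 0.095 or 0.12.
- Concurrent placebo, 0.6%: risk ratio (11/349)/(1/173) = 5.5, 95% CI 0.7 to 41.9; two-sided Fisher p = 0.12.
- Deaths: 1.4% lies inside 0% to 1.9%, so that statement agrees with its source.

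**Why a crude percentage will not serve in the extension.** Suppose a constant rate r and follow-up of t years. The expected proportion with at least one event is 1 − exp(−r·t). The documents give no rate per patient-year, so I assume r = 1.4 to 2.1 per 100 patient-years.

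| Follow-up | r = 1.4 | r = 2.1 |
|---|---|---|
| 1 year | 1.4% | 2.1% |
| 2 years | 2.8% | 4.1% |
| 4 years | 5.4% | 8.1% |

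The same underlying rate gives percentages that differ about fourfold between 1 and 4 years. A crude figure from the extension could fall below, inside or above 2.5% to 4.4% because of duration alone. That range is itself quoted without a time unit.

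**The case against.** The strongest reply is that this is loose background wording and no planned analysis is wrong. Much of that stands. Section 1.3.7 already words the comparison correctly and lacks only the interval. A descriptive incidence is ordinary in a single-arm safety study. The randomised evidence on pneumonia will come from the parent trials, planned at about 750 patients per arm.

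Four stronger readings are tempting, and the documents do not support them.

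- **That the protocol dismisses the signal.** It does not. Section 1.2.3.5 reports the imbalance just before the quoted sentence, Section 1.2.3.3 admits limited precision, and Section 5.2.3 makes pneumonia an event of special interest with 24-hour reporting and chest X-ray.
- **That Phase II would have missed a doubling about four times in five.** A two-sided Fisher test at 0.05 with 349 versus 173 does miss a doubling from 2.0% or 2.1% with probability 82% or 81%. That describes the comparison with concurrent placebo, whereas the quoted sentence refers to an external range. Against a fixed 2.0% or 2.1% (one-sided 0.025) the figure is 47% or 39%. The low placebo count may also explain part of the imbalance, since Section 1.2.3.3 calls the 0.6% slightly low.
- **That the statement beginning "Importantly, there was no relationship between steady-state exposure" rests on a handful of pneumonia cases per cohort.** The statement covers safety events in general, and the protocol does not split the 11 cases by dose cohort.
- **That the extension could support a rule declaring no excess if the rate ratio's upper limit is below 2.** Assume 1100 to 1750 patient-years in the extension, 1100 to 1300 on parent-study placebo, the rates above and no true excess. The limit would then fall below 2 only about 49% to 76% of the time. The comparison is also non-randomised, among completers, and Section 4.1.2 excludes patients who stopped permanently for safety reasons.

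What remains is the conflict between sections and the lack of an exposure-adjusted rate.

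**Conclusion.** The point holds, for pneumonia only. Sections 1.2.3 and 1.2.3.5 conflict with Sections 1.2.3.3 and 1.3.7. A rate of 3.2% (95% CI 1.6% to 5.6%) is within the cited general-elderly range, above the cited AD-trial rates of 2.0% and 2.1%, and above concurrent placebo at 0.6%. A reader might infer that crenezumab has been shown to raise pneumonia rates above those of AD trials. That does not follow, because the lower limit is below 2.0% and the placebo comparison gives p = 0.12. Nor does the point extend to deaths.

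For the extension, the incidence in Section 6.4 could not be compared with a benchmark or with the parent-study period, because follow-up varies up to about 4 years. This part has practical consequences, since rewording the background alone changes nothing the trial does.

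The conclusion assumes one case per patient and reads incidence in Section 6.4 as a proportion of patients, since no person-time is mentioned. The fourfold spread over duration also assumes a constant event rate.

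**What to change.** 1. In Sections 1.2.3 and 1.2.3.5, separate pneumonia from deaths. State that pneumonia occurred in 3.2% (95% CI 1.6% to 5.6%) on crenezumab versus 0.6% on placebo, within the cited range for elderly people in general but above the cited AD-trial rates, so that an excess is neither established nor excluded. Add the interval to Sections 1.2.3.3 and 1.3.7. Reconcile the source of the 2.5% to 4.4% range, which these two sections credit to different references, and state its time unit. The sentence on deaths can stay.

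2. In Section 6.4, add serious and total pneumonia in the extension per 100 patient-years with exact 95% CIs, by parent-study treatment group. Beside it, show the placebo-period rate from BN29552 and BN29553 under the same case definition. Label that comparison descriptive, non-randomised and completer-selected, and attach no margin or no-excess rule.

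3. Define the time at risk after the last dose for the patient-year denominator. Sections 5.3.1 and 5.6 use 16 weeks for adverse events, while Section 5.4.2.2 uses 8 weeks for events of special interest. These need to be reconciled first.

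The cost is some rewording and one added table from data already collected. The Phase II statement becomes less favourable, and the side-by-side rates may be over-read unless clearly labelled.
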